9.1.2 Superiority Analysis

Superiority will be assessed through continuity-corrected Z-tests comparing each active treatment to placebo. If both the test and RLD success proportions are statistically significantly greater than the placebo proportion (p<0.05) then they will be considered superior to the placebo. The results in the mITT population will be considered definitive and those in the PP population will be considered supportive.

For each treatment (Test and RLD) the Hypothesis to be tested is:

 $H_0: p_t - p_p \leq 0$

 $H_a: p_t - p_p > 0$

Where p_t = Proportion of cure for Treatment, and p_p is proportion of cure for Placebo.

The rest of the formulation is the similar to the one for Equivalence assessment, using 95% Confidence Interval. For testing the superiority, the following SAS code will be used:

proc freq data = dataset;

Confidential

```
tables treat*outcome/ riskdiff (Equal correct);
run;
```

10 SAFETY ANALYSES

10.1 Safety Endpoints

The reporting of safety data is descriptive, and it will include all subjects who receive at least one dose of investigational product. The variables for safety endpoints are AEs, Local Application Site Reactions and vital signs measurements. Safety data will be summarized by treatment group and time point of collection, when appropriate.

Concomitant medications will be coded using the World Health Organization Drug Dictionary (WHO-DD). These data will be summarized by treatment group. Previous and concomitant medications will be presented in a data listing.

10.1.1 Adverse Events

Adverse events will be coded using the most recent version of the Medical Dictionary for Regulatory Activities (MedDRA) and will be summarized based on frequency and severity of AEs for all treated subjects. Data will be summarized using preferred term and system organ classifications. Summary will show number and percentage of subjects who experience each AE.

If a subject experiences multiple events that map to a single preferred term, the greatest severity and strongest Investigator assessment of relation to study drug will be assigned to the preferred term for the appropriate summaries. Should an event have a missing severity or relationship, it will be classified as having the highest severity and/or strongest relationship to study drug.

Summaries of treatment-emergent AEs will include any AEs reported beginning with the first dose of study drug on Day 1. The occurrence of treatment-emergent adverse events will be summarized by treatment group using preferred terms, system organ classifications, and severity. Separate summaries of treatment-emergent serious adverse events, treatment-emergent adverse events related to study drug, and events leading to the discontinuation of study drug will be generated. All adverse events reported will be listed for individual subjects showing both verbatim and preferred terms.

Confidential

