2.1.2 Secondary Objective

To demonstrate safety of Podofilox Topical Gel 0.5% compared to Condylox® Gel 0.5% and placebo assessed by the frequency and severity of adverse events, and application site reaction scores (erythema, dryness, burning/stinging, erosion, edema, pain, itching and bleeding).

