7.4 Adverse Event Collection Period

Any AE/SAE prior to the Screening visit will be considered past medical history (PMH). The AE reporting period for this study begins with the signature of the Informed Consent Form and, for unresolved AEs, ends 30 days following the last study medication application. Those events that occur during the screening period and up to the day of the first application of the study drug will be considered Non-Treatment Emergent AEs.

Adverse events that occur during the treatment period (starting from the day of the first application of Study Drug and up to the final protocol required visit) will be considered Treatment Emergent AEs (TEAEs).

SAE(s) that are observed or spontaneously reported during the subject's participation in the trial will be captured and monitored until the Investigator deems the event to be chronic or not clinically significant or the subject to be stable.

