5 STUDY DESIGN

5.1 Summary of Study Design

This is a multicenter, parallel group, randomized, double-blind, placebo-controlled trial with clinical endpoint comparing Podofilox Topical Gel 0.5% to Condylox[®] Gel 0.5% and a matching placebo. The study will be conducted among adult male and female patients with external anogenital warts.

On the following day after the Baseline visit (Day 1) the subject will apply the study drug on EAWs following the recommendations given during training at the clinic site. The treatment phase will consist of four weekly treatment cycles at a maximum, during which the drug will be applied twice a day (in the morning and at the bedtime) for 3 consecutive days, then discontinuing for 4 consecutive days. Study drug will thus be applied only on Days 1, 2, 3, 8, 9, 10, 15, 16, 17, 22, 23 and 24.

Study visits will occur on the seventh (7) day of each treatment cycle: on Day 7 (Week 1), Day 14 (Week 2), Day 21 (Week 3), and Day 28 (Week 4). Primary endpoint (total disappearance of all treated warts) will be evaluated during each of these visits. In case the primary endpoint is reached at any of the visits prior to the Day 28 visit, it will be considered the End of Study (EOS) visit – the Investigator will perform physical examination and repeat urine pregnancy test, and subject's participation will be considered complete. If total disappearance of warts is not achieved, a new treatment cycle will be initiated for a maximum of four cycles in total for the subject.

During each study visit, the Investigator will collect vital signs, evaluate EAWs for absence or presence, capturing the count of EAWs, record Local Application Site Reactions and adverse events (AEs), assess Patient's Diary Card completion and subject's compliance with the study drug application, review concomitant medication and confirm that there were no prohibited therapies applied since the last visit.

In the event the primary endpoint (total disappearance of all warts within all treated areas) has been achieved prior to the Day 28 visit, this visit will be considered End of Study (EOS) visit. In case a subject discontinues prematurely, the Investigator will conduct an Early Termination (ET) visit, capturing the reason for discontinuation and performing assessments of EOS visit.

Protocol: 16-POD-001 Version 2.0, 15-Jan-2018

Confidential

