	from Baseline	Absent	xx (xx.x)	xx (xx.x)	xx (xx.x)	xx (xx.x)
		Present	xx (xx.x)	xx (xx.x)	xx (xx.x)	xx (xx.x)
		Mild	xx (xx.x)	xx (xx.x)	xx (xx.x)	xx (xx.x)
		Moderate	xx (xx.x)	xx (xx.x)	xx (xx.x)	xx (xx.x)
		Severe	xx (xx.x)	xx (xx.x)	xx (xx.x)	xx (xx.x)

Table 14.3.7Summary of Site Reaction by Intensity and Visit, Safety Population

Repeat for Site reactions: dryness, burning/stinging, erosion, edema, pain, itching, and bleeding.

Then Repeat for visit 4, 5, 6 and EOS.

n: number of patients affected. Test Product: Podofilox Topical Gel 0.5% Reference: Condylox® Gel 0.5% Placebo: vehicle that matches the test product

Source: <Dataset>

Program Name: <Pgm name>

Listing: 16.3.7 Date: YYYY-MM-DD Time: HH:MM:SS

Protocol: 16-POD-001 Version 2.0, 15-Jan-2018

Confidential

	Overall Summary o	of Adverse Events, Safe	ety Population	
	Test Product (N=xxx) n (%)	Reference (N=xxx) n (%)	Placebo (N=xxx) n (%)	All Subjects (N=xxx) n (%)
Total number of AEs	XX	XX	XX	XX
Total number of SAEs	XX	XX	XX	XX
Total Number of TEAEs	XX	XX	XX	XX
Total Number of TESAEs	XX	XX	XX	XX
Number of Subjects with:				
At Least One TEAE	xx (xx.x)	xx (xx.x)	xx (xx.x)	xx (xx.x)
At Least One Related TEAE	xx (xx.x)	xx (xx.x)	xx (xx.x)	xx (xx.x)
At Least One Severe TEAE	xx (xx.x)	xx (xx.x)	xx (xx.x)	xx (xx.x)
At Least One TEAE Leading to				
Discontinuation	xx (xx.x)	xx (xx.x)	xx (xx.x)	xx (xx.x)
At Least One TEAE Leading to			× ,	
Death	xx (xx.x)	xx (xx.x)	xx (xx.x)	xx (xx.x)
At Least One TESAE	xx (xx.x)	xx (xx.x)	xx (xx.x)	xx (xx.x)
At Least One Related TESAE	xx (xx.x)	xx (xx.x)	xx (xx.x)	xx (xx.x)
At Least One Severe TESAE	xx (xx.x)	xx (xx.x)	xx (xx.x)	xx (xx.x)
At Least One TESAE Leading to		. ,		
Discontinuation	xx (xx.x)	xx (xx.x)	xx (xx.x)	xx (xx.x)

Table 14 3 8

(S)AE: (Serious) Adverse Event reported from signature of the Informed Consent Form to 30 days following the last study drug application. TE(S)AE: Treatment Emerging (Serious) Adverse Event reported during the treatment period (from the day of the first application of the study drug and up to the last visit). Test Product: Podofilox Topical Gel 0.5% Reference: Condylox® Gel 0.5% Placebo: vehicle that matches the test product

Source: <dataset></dataset>	Listings: 16.3.8.1 – 16.3.8.2 – 16.3.8.3	Snapshot Data DD-MMM-YYYY
Program Name: <pgm name=""></pgm>	Date: YYYY-MM-DD Time: HH:MM:SS	Programmer: < Programmer Initials>

Protocol: 16-POD-001 Version 2.0, 15-Jan-2018

Confidential

Table 14.3.8.1.1

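### Cumulative TEAE percentages cover less exposure and observation time in arms that clear more; a cycle 1 table would compare arms over the same period

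*SAP*

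**What the plan says.** - **When observation ends.** SAP section 5.1 says that if clearance "has been achieved prior to the Day 28 visit, this visit will be considered End of Study (EOS) visit". The physical examination and pregnancy test are then done and "subject's participation will be considered complete". Protocol section 6.2.1.8 runs the AE questioning through the EOS/ET visit.
- **TEAE window.** Protocol section 7.4 counts events "starting from the day of the first application of Study Drug and up to the final protocol required visit". The footnote to SAP Table 14.3.8 agrees: "from the day of the first application of the study drug and up to the last visit". The 30-day extension in protocol section 7.4 is for AEs still unresolved.
- **Summary statistic.** SAP section 10.1.1: "Summary will show number and percentage of subjects who experience each AE". SAP section 7.4 takes percentages over all subjects in the treatment group. The shells for Tables 14.3.8 to 14.3.8.2 have no person-time, cycle or visit dimension.
- **Use.** The secondary objective (protocol section 2.1.2) compares the test gel with the RLD and placebo, "assessed by the frequency and severity of adverse events".
- **Expected clearance.** SAP section 5.3 plans on 40% success in each active arm and 15% on placebo.

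**The concern.** The efficacy outcome sets the length of safety observation. A subject who clears at Visit 3 contributes about 7 days, and one who completes without clearing contributes about 28. The SAP itself expects clearance to differ between active and placebo, so unequal time at risk is the planned situation and not an accident of conduct.

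A crude percentage over unequal periods cannot tell a lower event rate from a shorter period of dosing and observation. A reader of the TEAE tables could credit an active gel with better tolerability per application when some or all of the difference comes from stopping sooner. Because protocol section 6.2.1.7 requires every application site reaction to be recorded as an AE, these tables also carry the local tolerability signal.

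**Working it through.** The plan states no figure for safety follow-up or person-time, so there is none to reproduce. The check asks what the planned tables would show if every arm had the same event hazard while on study.

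**Inputs from the documents.** Clearance p = 0.40 (active) and 0.15 (placebo), and 177:177:59 randomised (SAP section 5.3). Visits on Days 7, 14, 21 and 28 (SAP section 5.1).

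**Assumptions.** The documents do not give clearance timing or the vehicle AE rate. I take clearing as spread evenly over the four visits, a 40% risk over four weeks with identical hazards in all arms, visits on their nominal days and no early termination.

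**Step 1: observation time.** The mean clearance day is (7 + 14 + 21 + 28)/4 = 17.5. Mean days = (1 − p) × 28 + p × 17.5.
- Active: 0.60 × 28 + 0.40 × 17.5 = 23.8 days.
- Placebo: 0.85 × 28 + 0.15 × 17.5 = 26.4 days, a ratio of 0.90.
- Still observed in week 4: 1 − 0.40 × 0.75 = 70% of active and 1 − 0.15 × 0.75 = 89% of placebo subjects.
- Extremes: if all clearing is at Day 7, 19.6 v 24.9 days (ratio 0.79). If all is at Day 28, 28 v 28 (ratio 1.00).

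**Step 2: crude percentages.** Let I1 to I4 be the cumulative risk by the end of weeks 1 to 4, and M their mean. Crude percentage = (1 − p) × I4 + p × M, so the gap is (0.40 − 0.15) × (I4 − M).
- *Constant hazard.* Ik = 1 − 0.6^(k/4) = 0.120, 0.225, 0.318, 0.400, so M = 0.266. Active: 0.60 × 0.400 + 0.40 × 0.266 = 34.6%. Placebo: 0.85 × 0.400 + 0.15 × 0.266 = 38.0%. Gap 3.4 points.
- *Front-loaded, 45/45/5/5% of hazard by week.* Ik = 0.205, 0.369, 0.385, 0.400, so M = 0.340. Active 37.6%, placebo 39.1%. Gap 1.5 points.

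Gap (placebo minus active, in points) by clearance timing over Visits 3 to 6:

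| Timing of clearance | Constant hazard | Front-loaded |
|---|---|---|
| 50/25/15/10% | 4.9 | 2.7 |
| Even | 3.4 | 1.5 |
| 10/20/30/40% | 2.2 | 0.8 |
| All at Day 28 | 0 | 0 |

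**Step 3: test against RLD.** At the planned 40% in both arms with the same timing the gap is zero. If clearance were 45% v 35%, it would be 0.10 × (0.400 − 0.266) = 1.3 points under constant hazard and 0.10 × (0.400 − 0.340) = 0.6 points front-loaded.

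**Step 4: would a rate per subject-week correct it?** Take subjects with a first event, divided by weeks to first event or exit. Under constant hazard the active:placebo ratio is 1.00, as it should be. Now take the front-loaded case with even timing.
- Total hazard is −ln 0.6 = 0.511, so the weekly hazards h are 0.230, 0.230, 0.026, 0.026.
- Event-free proportions S are 1, 0.795, 0.631, 0.615, 0.600. Weeks at risk within week k are (S at start − S at end)/h, which cumulate to 0.894, 1.604, 2.227, 2.834, with mean 1.890.
- Active: 0.60 × 2.834 + 0.40 × 1.890 = 2.456 weeks, rate 0.376/2.456 = 0.153.
- Placebo: 0.85 × 2.834 + 0.15 × 1.890 = 2.693 weeks, rate 0.391/2.693 = 0.145.
- Rate ratio 1.05, against a crude ratio of 0.376/0.391 = 0.96. The true hazards are identical, so the rate shows a false active excess of about the same size as the crude deficit.

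**Step 5: cycle 1 only.** Clearing cannot end observation before Visit 3. The risk to that visit is I1 in every arm (12.0% constant, 20.5% front-loaded), and the gap is zero under either hazard pattern and any clearance timing.

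**Step 6: scale.** With all 177 and 59 subjects treated, the standard error of 34.6% v 38.0% is √(0.346 × 0.654/177 + 0.380 × 0.620/59) = 7.3 points. A 3.4-point gap is under half of one standard error.

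**The case against.** - **The crude figure is a legitimate quantity.** Dosing stops when observation stops, and each nominal visit falls about four days after that cycle's last application. For drug-caused events, a subject who skips later cycles really does have less risk. This stands. A reader might infer that the whole gap is spurious, but the documents do not support that.
- **The main comparison is untouched under the plan.** This stands at 40% v 40% with equal timing. A reader might infer a built-in safety bias between test and RLD, but nothing in the plan implies one unless clearance rate or timing differs.
- **Not every non-clearer reaches Day 28.** This stands. Protocol section 4.2 lists other reasons to discontinue, section 6.3.4 brings the ET visit forward, and the final window is ±5 days. Discontinuation for worsening would shorten observation among non-clearers, possibly more on placebo. The documents give no rates, so even the net direction is not certain.
- **Events come early.** Protocol section 1.2.3 reports this for severe reactions on the reference gel. It roughly halves the even-timing gap but does not remove it.
- **Other tables help.** Site reactions are tabulated by visit (Table 14.3.7) and exposure by week (Tables 14.3.3 to 14.3.5). Neither covers other AEs, causality or discontinuation, and neither is linked to the TEAE percentages. SAP section 10.1 allows summaries by time point where appropriate, but no TEAE shell uses this.
- **Safety reporting is descriptive.** True: no test or margin depends on these percentages. That limits the consequence, though the secondary objective still compares them.

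**Conclusion.** The point holds in a limited form. The cumulative TEAE tables compare active with placebo over unequal dosing and observation, and cannot separate a lower event rate from a shorter course. The illustrative size is 3.4 points under constant hazard and about 1.5 points with early events, both at even clearance timing. It ranges from 0 to 4.9 points over the timings in the table. These figures rest on assumed timing, identical hazards in all arms and no early termination. The front-loaded figure is nearer to what the protocol reports for severe reactions.

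A reader might conclude that the plan makes the active gels look safer than they are. The documents show only that the percentages are hard to interpret. Part of the gap is real, its size is modest, and early termination could offset it. This is a worthwhile improvement, not a defect that threatens the trial's conclusions.

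**What to change.** - **SAP section 10.1.1.** Keep the crude tables, and state that they describe risk under treatment until clearance, over a period that differs between subjects.
- **Add one table.** TEAEs (any, related, severe) by arm, with onset from first application to Visit 3. Subjects who leave before Visit 3 for other reasons should be counted in a footnote. SAP section 7.6.7 can set a missing onset date to the first dose, so also report how many events enter through imputed dates.
- **Optional.** TEAE incidence in each later cycle among subjects still under observation, with that denominator shown and labelled descriptive, since those subjects are selected by not having cleared.
- **Do not** use a single events-per-subject-week rate as the correction. It is biased against the faster-clearing arm when events are front-loaded (Step 4).
- **Reconcile the windows.** Table 14.3.8.1.1 is titled as a TEAE table, but its footnote defines AEs up to 30 days after the last application. Protocol section 7.4 and the Table 14.3.8 footnote end the TEAE window at the final visit.

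The cost is some SAP wording and one table from AE onset, application and visit dates already collected. The downside is precision. Under constant hazard the cycle 1 table would hold about 0.120 × 177 = 21 subjects with an event per active arm, against 0.346 × 177 = 61 in the crude table, and about 0.120 × 59 = 7 on placebo.

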10.1.2 Local Application Site Reactions

Local Application Site Reactions will be recorded at each study visit and will be summarized by the type of reaction (erythema, dryness, burning/stinging, erosion, edema, pain, itching and bleeding) and intensity score: 0=absent, 1=mild (slight, barely perceptible), 2=moderate (distinct presence), 3=severe (marked, intense The number and percentage of subjects affected will also be presented.

10.1.3 Vital Signs

Vital Signs will be examined at several visits as per schedule on Section 3.2 above and will be summarized by visit and by treatment group.

STATISTICAL ANALYSIS PLAN

Confidential

12 APPENDIX

12.1 APPENDIX A. Tables and Listings

12.1.1 List of Tables

Display Number	Title	Population	Unique/Repeat
C to a day			
Population			
Table 14.1.1.1.1	Subject Disposition	All Subjects	Unique
Table	Subject Enrollment and Disposition	All Subjects	Unique
14.1.1.1.2.1			
Table	Subject Enrollment and Disposition,	All Subjects	Repeat
14.1.1.1.2.2	Supplemental (including site 201)		
Table 14.1.1.1.3	Subject Disposition by Site and Treatment	All Subjects	Unique
Table 14.1.1.2	Randomized Subjects Not Included in Safety, PP. and mITT Populations by Treatment	All Subjects	Unique
Table 14.1.2.1	Summary of Protocol Deviations by	Safety	Unique
	Classification and Category	Population	1
Table 14.1.2.2	Summary of Protocol Deviations by	Safety	Repeat
	Classification and Category Supplemental	Population	1
	(including site 201)	-	
Table 14.1.3.1.1	Summary of Demographic	mITT	Unique
Table 14.1.3.1.2	Summary of Demographic	PP	Repeat
Table 14.1.3.1.3	Summary of Demographic	Safety	Repeat
Efficacy Tables		-	_
Table 14.2.1.1.1	Summary of Treatment Success by Visit	PP	Unique
Table 14.2.1.1.2	Summary of Treatment Success by Visit,	PPs	Repeat
	Supplemental (including site 201)		-
Table 14.2.1.2.1	Summary of Treatment Success by Visit	mITT	Repeat
Table 14.2.1.2.2	Summary of Treatment Success by Visit,	mITTs	Repeat
	Supplemental (including site 201)		
Table 14.2.2.1.1	Treatment Success, Bioequivalence Test	PP/mITT	Unique
	between Test Product and Reference		_

Protocol: 16-POD-001 Version 2.0, 15-Jan-2018

Confidential

Display Number	Title	Population	Unique/Repeat
Table 14.2.2.1.2	Treatment Success, Bioequivalence Test	PPs/mITTs	Repeat
	between Test Product and Reference,		-
	Supplemental (including site 201)		
Table 14.2.3.1.1	Treatment Success, Superiority Test from	mITT/PP	Unique
	Placebo		
Table 14.2.3.1.2	Treatment Success, Superiority Test from	mITTs/PPs	Repeat
	Placebo, Supplemental (including site 201)		
Table 14.2.4.1.1	Number of Genital Warts by Visit	PP	Unique
Table 14.2.4.1.2	Number of Genital Warts by Visit,	PPs	Repeat
	Supplemental (including site 201)		
Table 14.2.4.2.1	Number of Genital Warts by Visit	mITT	Repeat
Table 14.2.4.2.2	Number of Genital Warts by Visit,	mITTs	Repeat
	Supplemental (including site 201)		
Table 14.2.5.1.1	Number of Perianal Warts by Visit	PP	Unique
Table 14.2.5.1.2	Number of Perianal Warts by Visit,	PPs	Repeat
	Supplemental (including site 201)		
Table 14.2.5.2.1	Number of Perianal Warts by Visit	mITT	Repeat
Table 14.2.5.2.2	Number of Perianal Warts by Visit,	mITTs	Repeat
	Supplemental (including site 201)		
Table 14.2.6.1.1	Number of Genital and Perianal Warts by	PP	Unique
	Visit		
Table 14.2.6.1.2	Number of Genital and Perianal Warts by	PPs	Repeat
	Visit, Supplemental (including site 201)		
Table 14.2.6.2.1	Number of Genital and Perianal Warts by	mITT	Repeat
	Visit		
Table 14.2.6.2.2	Number of Genital and Perianal Warts by	mITTs	Repeat
	Visit, Supplemental (including site 201)		
Table 14.2.7.1.1	Warts Area (cm ²) by Visit	PP	Unique
Table 14.2.7.1.2	Warts Area (cm ²) by Visit, Supplemental	PPs	Repeat
	(including site 201)		
Table 14.2.7.2.1	Warts Area (cm ²) by Visit	mITT	Repeat
Table 14.2.7.2.2	Warts Area (cm ²) by Visit, Supplemental	mITTs	Repeat
	(including site 201)		
Safety			
Table 14.3.1.1	Summary of Vital Sign	Safety	Unique

Protocol: 16-POD-001 Version 2.0, 15-Jan-2018

Confidential

Display Number		Population	Unique/Repeat
Table 14.3.1.2	Vital Signs Changes from Baseline	Safety	Unique
Table 14.3.2	Summary of Physical Examination	Safety	Unique
Table 14.3.3	Summary of Study Drug Exposure, Dose in	Safety	Unique
	grams by Week		
Table 14.3.4.1	Summary of Study Drug Exposure, Number	Safety	Unique
	of Applications by Week		
Table 14.3.4.2	Summary of Study Drug Exposure, Duration	Safety	Unique
	of Exposure in Hours by Week		
Table 14.3.5	Summary of Treatment Compliance (%) by	Safety	Unique
	Week		
Table 14.3.6	Summary of Concomitant Medications by	Safety	Repeat
	Preferred Term		
Table 14.3.7	Summary of Site Reaction by Intensity and	Safety	Unique
	Visit		
Table 14.3.8	Overall Summary of Adverse Events	Safety	Unique
Table 14.3.8.1.1	Summary of Treatment Emergent Adverse	Safety	Unique
	Events (TEAEs) by System Organ Class and		
	Preferred Term		
Table 14.3.8.1.2	Summary of Treatment Emergent Adverse	Safety	Unique
	Events (TEAEs) by System Organ Class,		
	Preferred Term, and Severity		
Table 14.3.8.1.3	Summary of Treatment Emergent Adverse	Safety	Repeat
	Events (TEAEs) by System Organ Class,		
	Preferred Term, and Causality		
Table 14.3.8.2	Summary of Treatment Emergent Serious	Safety	Unique
	Adverse Events (TESAEs) by System Organ		
	Class and Preferred Term		

Confidential

Table 14.1.1.1.1 Subject Disposition, All Subjects

Population	Test Product n (%)	Reference n (%)	Placebo n (%)	All Subjects n (%)
All Subjects	xx (xx.x)	xx (xx.x)	xx (xx.x)	xx (xx.x)
Safety Population	xx (xx.x)	xx (xx.x)	xx (xx.x)	xx (xx.x)
mITT Population	xx (xx.x)	xx (xx.x)	xx (xx.x)	xx (xx.x)
PP Population	xx (xx.x)	xx (xx.x)	xx (xx.x)	xx (xx.x)
Test Product: Dedefiley Terrical Cal 0.4	50/			 

Test Product: Podofilox Topical Gel 0.5% Reference: Condylox[®] Gel 0.5% Placebo: vehicle that matches the test product

Source: <Dataset>

Listing: 16.1.1.1

Program Name: <Pgm name>

Date: YYYY-MM-DD Time: HH:MM:SS

Snapshot Data: DD-MMM-YYYY

Programmer: < Programmer Initials>

Protocol: 16-POD-001 Version 2.0, 15-Jan-2018

Confidential

Table 14.1.1.1.2.1Subject Enrollment and Disposition, All Subjects

Disposition	Test Product n (%)	Reference n (%)	Placebo n (%)	All Subjects n (%)
Screened				xx (xx.x)
Randomized	xx (xx.x)	xx (xx.x)	xx (xx.x)	xx (xx.x)
Treated	xx (xx.x)	xx (xx.x)	xx (xx.x)	xx (xx.x)
Completed Study	xx (xx.x)	xx (xx.x)	xx (xx.x)	xx (xx.x)
Completed Day 0 (Baseline)	xx (xx.x)	xx (xx.x)	xx (xx.x)	xx (xx.x)
Completed Day 7 (Visit 3)	xx (xx.x)	xx (xx.x)	xx (xx.x)	xx (xx.x)
Completed Day 14 (Visit 4)	xx (xx.x)	xx (xx.x)	xx (xx.x)	xx (xx.x)
Completed Day 21 (Visit 5)	xx (xx.x)	xx (xx.x)	xx (xx.x)	xx (xx.x)
Completed Day 28 (Visit 6)	xx (xx.x)	xx (xx.x)	xx (xx.x)	xx (xx.x)
Discontinued	xx (xx.x)	xx (xx.x)	xx (xx.x)	xx (xx.x)
Screen Failure				xx (xx.x)
Withdrawal of consent by subject	xx (xx.x)	xx (xx.x)	xx (xx.x)	xx (xx.x)
Withdrawal of subject by Investigator's Decision	xx (xx.x)	xx (xx.x)	xx (xx.x)	xx (xx.x)
Pregnancy	xx (xx.x)	xx (xx.x)	xx (xx.x)	xx (xx.x)
Occurrence of an Adverse Event (AE) or Serious Adverse Event (SAE) Significant non-compliance with study	xx (xx.x)	xx (xx.x)	xx (xx.x)	xx (xx.x)
procedures	xx (xx.x)	xx (xx.x)	xx (xx.x)	xx (xx.x)
Treatment failure	xx (xx.x)	xx (xx.x)	xx (xx.x)	xx (xx.x)

Protocol: 16-POD-001 Version 2.0, 15-Jan-2018

Confidential

Disposition	Test Product n (%)	Reference n (%)	Placebo n (%)	All Subjects n (%)
Subject's medication code unblinded	xx (xx.x)	xx (xx.x)	xx (xx.x)	xx (xx.x)
Subject no longer meets the entry criteria	xx (xx.x)	xx (xx.x)	xx (xx.x)	xx (xx.x)
Lost of follow-up	xx (xx.x)	xx (xx.x)	xx (xx.x)	xx (xx.x)
Investigator discretion	xx (xx.x)	xx (xx.x)	xx (xx.x)	xx (xx.x)
Other	xx (xx.x)	xx (xx.x)	xx (xx.x)	xx (xx.x)

Test Product: Podofilox Topical Gel 0.5% Reference: Condylox® Gel 0.5% Placebo: vehicle that matches the test product

Source: <Dataset> Program Name: <Pgm name> Listing: 16.1.1.1 Date: YYYY-MM-DD Time: HH:MM:SS Snapshot Data DD-MMM-YYYY Programmer: <Programmer Initials>

Repeat as Supplemental Analysis including site 201

Protocol: 16-POD-001 Version 2.0, 15-Jan-2018

Confidential

Table 14.1.1.3Subject Disposition by Site and Treatment, All Subjects

		Test Product	Reference	Placebo	All Subjects
Site	Disposition	n (%)	n (%)	n (%)	n (%)
101	Screened				xx (xx.x)
	Screen failure				xx (xx.x)
	Randomized	xx (xx.x)	xx (xx.x)	xx (xx.x)	xx (xx.x)
	Treated	xx (xx.x)	xx (xx.x)	xx (xx.x)	xx (xx.x)
	Completed	xx (xx.x)	xx (xx.x)	xx (xx.x)	xx (xx.x)
	Discontinued	xx (xx.x)	xx (xx.x)	xx (xx.x)	xx (xx.x)

Repeat for each site

Test Product: Podofilox Topical Gel 0.5% Reference: Condylox® Gel 0.5% Placebo: vehicle that matches the test product

Source: <Dataset> Program Name: <Pgm name> Listing: 16.1.1.1 Date: YYYY-MM-DD Time: HH:MM:SS

Protocol: 16-POD-001 Version 2.0, 15-Jan-2018

Confidential

Table 14.1.1.2 Randomized Subjects Not Included in Safety, PP, and mITT Populations by Treatment, All Subjects

	Statistic	Test Product	Reference	Placebo	All Subjects
Randomized	Ν	XX	XX	XX	XX
Total Safety Population	n (%)	xx (xx.x)	xx (xx.x)	xx (xx.x)	xx (xx.x)
Total exclusion from Safety population	n (%)	xx (xx.x)	xx (xx.x)	xx (xx.x)	xx (xx.x)
Reason for exclusion from Safety	n (%)	xx (xx.x)	xx (xx.x)	xx (xx.x)	xx (xx.x)
No record of first dose	n (%)	xx (xx.x)	xx (xx.x)	xx (xx.x)	xx (xx.x)
Total mITT Population	n (%)	xx (xx.x)	xx (xx.x)	xx (xx.x)	xx (xx.x)
Total exclusion from mITT population	n (%)	xx (xx.x)	xx (xx.x)	xx (xx.x)	xx (xx.x)
Reason for exclusion from mITT	n (%)	xx (xx.x)	xx (xx.x)	xx (xx.x)	xx (xx.x)
No record of first dose	n (%)	xx (xx.x)	xx (xx.x)	xx (xx.x)	xx (xx.x)
No post-treatment data	n (%)	xx (xx.x)	xx (xx.x)	xx (xx.x)	xx (xx.x)
[add additional items]	n (%)	xx (xx.x)	xx (xx.x)	xx (xx.x)	xx (xx.x)
Total PP Population	n (%)	xx (xx.x)	xx (xx.x)	xx (xx.x)	xx (xx.x)
Total exclusion from PP population	n (%)	xx (xx.x)	xx (xx.x)	xx (xx.x)	xx (xx.x)
Reason for exclusion from PP	n (%)	xx (xx.x)	xx (xx.x)	xx (xx.x)	xx (xx.x)
Enrolled in error	n (%)	xx (xx.x)	xx (xx.x)	xx (xx.x)	xx (xx.x)
Lost to follow-up	n (%)	xx (xx.x)	xx (xx.x)	xx (xx.x)	xx (xx.x)
Non-compliant (dosing)	n (%)	xx (xx.x)	xx (xx.x)	xx (xx.x)	xx (xx.x)
Outside visit window	n (%)	xx (xx.x)	xx (xx.x)	xx (xx.x)	xx (xx.x)
Randomized in error	n (%)	xx (xx.x)	xx (xx.x)	xx (xx.x)	xx (xx.x)
Restricted medication	n (%)	xx (xx.x)	xx (xx.x)	xx (xx.x)	xx (xx.x)
[add additional items]	n (%)	xx (xx.x)	xx (xx.x)	xx (xx.x)	xx (xx.x)

Test Product: Podofilox Topical Gel 0.5% Reference: Condylox® Gel 0.5%

Placebo: vehicle that matches the test product

Source: <Dataset> Program Name: <Pgm name> Listing: 16.1.1.2 Date: YYYY-MM-DD Time: HH:MM:SS

Protocol: 16-POD-001 Version 2.0, 15-Jan-2018

Confidential

Table 14.1.2.2Summary of Protocol Deviations by Classification and Category,
Safety Population

	Test Product	Reference	Placebo	All Subjects
Classification/Category	n (%)	n (%)	n (%)	n (%)
Number of patients with:				
At least one Major Deviation	xx (xx.x)	xx (xx.x)	xx (xx.x)	xx (xx.x)
At least one Minor Deviation	xx (xx.x)	xx (xx.x)	xx (xx.x)	xx (xx.x)
Number of Major Deviations	XX	XX	XX	XX
Subject Dosing	xx (xx.x)	xx (xx.x)	xx (xx.x)	xx (xx.x)
Inclusion/Exclusion criteria	xx (xx.x)	xx (xx.x)	xx (xx.x)	xx (xx.x)
[add additional items]	xx (xx.x)	xx (xx.x)	xx (xx.x)	xx (xx.x)
Number of Minor Deviations	XX	XX	XX	XX
Out of window	xx (xx.x)	xx (xx.x)	xx (xx.x)	xx (xx.x)
[add additional items]	xx (xx.x)	xx (xx.x)	xx (xx.x)	xx (xx.x)

n: Number of deviations, except for the two first lines where it is specified as number of patients.

Test Product: Podofilox Topical Gel 0.5%

Reference: Condylox® Gel 0.5%

Placebo: vehicle that matches the test product

Source: <Dataset> Program Name: <Pgm name> Listing: 16.1.2 Date: YYYY-MM-DD Time: HH:MM:SS

Protocol: 16-POD-001 Version 2.0, 15-Jan-2018

STATISTICAL ANALYSIS PLAN

Confidential

Table 14.1.3.1.1Summary of Demographics, mITT Population

		Test Product	Reference	Placebo	All Subjects
Variable	Statistic	N =	N=	N=	N =
Age	Ν	XX	XX	XX	XX
	Mean (SD)	xx.x (xx.xxx)	xx.x (xx.xxx)	xx.x (xx.xxx)	xx.x (xx.xxx)
	Min, Max	XX.X, XX.X	XX.X, XX.X	XX.X, XX.X	XX.X, XX.X
Sex	n				
Male	n (%)	xx (xx.x)	xx (xx.x)	xx (xx.x)	xx (xx.x)
Female		xx (xx.x)	xx (xx.x)	xx (xx.x)	xx (xx.x)
Ethnicity	n (%)				
Hispanic or Latino		xx (xx.x)	xx (xx.x)	xx (xx.x)	xx (xx.x)
Not Hispanic or Latino		xx (xx.x)	xx (xx.x)	xx (xx.x)	xx (xx.x)
Race	n (%)				
American Indian or Alaskan					
Native		xx (xx.x)	xx (xx.x)	xx (xx.x)	xx (xx.x)
Asian		xx (xx.x)	xx (xx.x)	xx (xx.x)	xx (xx.x)
Black or African American		xx (xx.x)	xx (xx.x)	xx (xx.x)	xx (xx.x)
Native Hawaiian or Other					
Pacific Islander		xx (xx.x)	xx (xx.x)	xx (xx.x)	xx (xx.x)
White		xx (xx.x)	xx (xx.x)	xx (xx.x)	xx (xx.x)
Other		xx (xx.x)	xx (xx.x)	xx (xx.x)	xx (xx.x)

Test Product: Podofilox Topical Gel 0.5% Reference: Condylox® Gel 0.5% Placebo: vehicle that matches the test product

Source: <Dataset>Listing: 16.1.3.1Snapshot Data DD-MMM-YYYYProgram Name: <Pgm name>Date: YYYY-MM-DD Time: HH:MM:SSProgrammer: <Programmer Initials>

Repeat for PP and Safety populations

Protocol: 16-POD-001 Version 2.0, 15-Jan-2018

Confidential

Table 14.2.1.1.1 Summary of Treatment Success by Visit, PP Population

	Test Product N =	Reference N =	Placebo N =	All Subjects N =
Visit	n (%)	n (%)	n (%)	n (%)
Visit 3 (Day 7)	xx (xx.xx)	xx (xx.xx)	xx (xx.xx)	xx (xx.xx)
Visit 4 (Day 14)	xx (xx.xx)	xx (xx.xx)	xx (xx.xx)	xx (xx.xx)
Visit 5 (Day 21)	xx (xx.xx)	xx (xx.xx)	xx (xx.xx)	xx (xx.xx)
Visit 6 (Day 28)	xx (xx.xx)	xx (xx.xx)	xx (xx.xx)	xx (xx.xx)
EOS	xx (xx.xx)	xx (xx.xx)	xx (xx.xx)	xx (xx.xx)

Treatment success: total disappearance of all warts within all treated areas.

Test Product: Podofilox Topical Gel 0.5%

Reference: Condylox® Gel 0.5%

Placebo: vehicle that matches the test product

Source: <dataset></dataset>	Listing: 16.2	Snapshot Data DD-MMM-YYYY
Program Name: <pgm name=""></pgm>	Date: YYYY-MM-DD Time: HH:MM:SS	Programmer: < Programmer Initials>

Protocol: 16-POD-001 Version 2.0, 15-Jan-2018

Confidential

Table 14.2.2.1.1 Bioequivalence Test for Proportion of Treatment Success between Test and Reference Products

		Test Product	Reference	Difference (SE)	90% CI
Population		n (%)	n (%)		
РР	EOS	xx (xx.xx)	xx (xx.xx)	x.xx (x.xxx)	(x.xx, x.xx)
mITT		xx (xx.xx)	xx (xx.xx)	x.xx (x.xxx)	(x.xx, x.xx)
n: Number of subjec	ts who experienced treatm	nent success			
SE: Standard Error					
CI: Confidence Inter	val				
Test Product: Podofi	lox Topical Gel 0.5%				

Reference: Condylox® Gel 0.5%

Source: <Dataset>

Program Name: <Pgm name>

Listing: 16.2 Date: YYYY-MM-DD Time: HH:MM:SS Snapshot Data DD-MMM-YYYY

Programmer: < Programmer Initials>

Repeat as Supplemental Analysis including site 201 for PPs/mITTs

Protocol: 16-POD-001 Version 2.0, 15-Jan-2018

Confidential

Table 14.2.3.1.1Treatment Success, Superiority Test from Placebo

	Test Productn (%)	Reference n (%)	Placebo n (%)	Test vs. Placebo Diff (95% CI) p	Reference vs. Placebo- Diff (95% CI)
mITT	xx (xx.xx)	xx (xx.xx)	xx (xx.xx)	x.xx (x.xx, x.xx) x.xxxx	x.xx (x.xx, x.xx)
PP	xx (xx.xx)	xx (xx.xx)	xx (xx.xx)	x.xx (x.xx, x.xx) x.xxxx	x.xx (x.xx, x.xx)

n: Number of subjects who experienced treatment success SE: Standard Error CI: Confidence Interval *p*: Probability of lower bound of CI with Walt-Yate's continuity correction Test Product: Podofilox Topical Gel 0.5% Reference: Condylox® Gel 0.5%

Source: <Dataset>Listing: 16.2Snapshot Data DD-MMM-YYYYProgram Name: <Pgm name>Date: YYYY-MM-DD THH:MM:SSProgrammer: <Programmer Initials>

Repeat as Supplemental Analysis including site 201 for PPs/mITTs

Protocol: 16-POD-001 Version 2.0, 15-Jan-2018

Confidential

Table 14.2.4.1.1Number of Genital Warts by Visit, PP Population

	Statistic	Test Product	Reference	Placebo	All Subjects
Visit	N =	N =	N =	N =	N =
Baseline (Day 0)	n	n (%)	n (%)	n (%)	n (%)
	Mean (SD)	xx.x (xx.xx)	xx.x (xx.xx)	xx.x (xx.xx)	xx.x (xx.xx)
	CV	XX.X	XX.X	XX.X	XX.X
	Median	XX.X	XX.X	XX.X	XX.X
	Min, Max	XX.X, XX.X	XX.X, XX.X	XX.X, XX.X	XX.X, XX.X
Visit 3 (Day 7)	n	n (%)	n (%)	n (%)	n (%)
	Mean (SD)	xx.x (xx.xx)	xx.x (xx.xx)	xx.x (xx.xx)	xx.x (xx.xx)
	CV	XX.X	XX.X	XX.X	XX.X
	Median	XX.X	XX.X	XX.X	XX.X
	Min, Max	XX.X, XX.X	XX.X, XX.X	XX.X, XX.X	XX.X, XX.X
Visit 3 change from	l				
baseline	n	n (%)	n (%)	n (%)	n (%)
	Mean (SD)	xx.x (xx.xx)	xx.x (xx.xx)	xx.x (xx.xx)	xx.x (xx.xx)
	CV	XX.X	XX.X	XX.X	XX.X
	Median	XX.X	XX.X	XX.X	XX.X
	Min, Max	XX.X, XX.X	XX.X, XX.X	XX.X, XX.X	XX.X, XX.X
Repeat for Visits 4,	5, 6 and EOS				
Test Product: Podot Reference: Condylo Placebo: vehicle tha	filox Topical Gel 0.5% px® Gel 0.5% at matches the test produ	ıct			
Source: <dataset></dataset>		Listing: 16.2		Snapshot	Data DD-MMM-YYYY
Program Name: <p< td="">gm name>	Date: YYYY-MM	I-DD Time: HH:MM:SS	Programmer	: <programmer initials=""></programmer>	</p<>	gm name>	Date: YYYY-MM	I-DD Time: HH:MM:SS	Programmer	: <programmer initials=""></programmer>

Protocol: 16-POD-001 Version 2.0, 15-Jan-2018

Confidential

Table 14.2.5.1.1Number of Perianal Warts by Visit, PP Population

		Test Product	Reference	Placebo	All Subjects
Visit	Statistic	N=	N=	N=	N=
Baseline (Day 0)	n	n (%)	n (%)	n (%)	n (%)
	Mean (SD)	xx.x (xx.xx)	xx.x (xx.xx)	xx.x (xx.xx)	xx.x (xx.xx)
	CV	XX.X	XX.X	XX.X	XX.X
	Median	XX.X	XX.X	XX.X	XX.X
	Min, Max	XX.X, XX.X	XX.X, XX.X	XX.X, XX.X	XX.X, XX.X
Visit 3 (Day 7)	n	n (%)	n (%)	n (%)	n (%)
	Mean (SD)	xx.x (xx.xx)	xx.x (xx.xx)	xx.x (xx.xx)	xx.x (xx.xx)
	CV	XX.X	XX.X	XX.X	XX.X
	Median	XX.X	XX.X	XX.X	XX.X
	Min, Max	XX.X, XX.X	XX.X, XX.X	XX.X, XX.X	XX.X, XX.X
Visit 3 change from					
baseline	n	n (%)	n (%)	n (%)	n (%)
	Mean (SD)	xx.x (xx.xx)	xx.x (xx.xx)	xx.x (xx.xx)	xx.x (xx.xx)
	CV	XX.X	XX.X	XX.X	XX.X
	Median	XX.X	XX.X	XX.X	XX.X
	Min, Max	XX.X, XX.X	XX.X, XX.X	XX.X, XX.X	XX.X, XX.X
Repeat for Visits 4,	5, 6 and EOS.				
Test Product: Podof Reference: Condylo Placebo: vehicle tha	ilox Topical Gel 0.5% x® Gel 0.5% t matches the test product				
Source: <dataset></dataset>		Listing: 16.2		Snapshot l	Data DD-MMM-YYYY
Program Name: <pg< td="">m name>	Date: YYYY-MM-I	DD Time: HH:MM:SS	Programmer	: <programmer initials=""></programmer>	</pg<>	m name>	Date: YYYY-MM-I	DD Time: HH:MM:SS	Programmer	: <programmer initials=""></programmer>

Protocol: 16-POD-001 Version 2.0, 15-Jan-2018

Confidential

Table 14.2.6.1.1	
Number of Genital and Perianal Warts by Visit, PP Population	

		Test Product	Reference	Placebo	All Subjects
Visit	Statistic	N=	N=	N=	N=
Baseline (Day 0)	n	n (%)	n (%)	n (%)	n (%)
	Mean (SD)	xx.x (xx.xx)	xx.x (xx.xx)	xx.x (xx.xx)	xx.x (xx.xx)
	CV	XX.X	XX.X	XX.X	XX.X
	Median	XX.X	XX.X	XX.X	XX.X
	Min, Max	XX.X, XX.X	XX.X, XX.X	XX.X, XX.X	XX.X, XX.X
Visit 3 (Day 7)	n	n (%)	n (%)	n (%)	n (%)
	Mean (SD)	xx.x (xx.xx)	xx.x (xx.xx)	xx.x (xx.xx)	xx.x (xx.xx)
	CV	XX.X	XX.X	XX.X	XX.X
	Median	XX.X	XX.X	XX.X	XX.X
	Min, Max	XX.X, XX.X	XX.X, XX.X	XX.X, XX.X	XX.X, XX.X
Visit 3 change from					
baseline	n	n (%)	n (%)	n (%)	n (%)
	Mean (SD)	xx.x (xx.xx)	xx.x (xx.xx)	xx.x (xx.xx)	xx.x (xx.xx)
	CV	XX.X	XX.X	XX.X	XX.X
	Median	XX.X	XX.X	XX.X	XX.X
	Min, Max	XX.X, XX.X	XX.X, XX.X	XX.X, XX.X	XX.X, XX.X
Repeat for Visits 4,	5, 6 and EOS.				
Test Product: Podof Reference: Condylc Placebo: vehicle tha	ilox Topical Gel 0.5% x® Gel 0.5% tt matches the test product				
Source: <dataset></dataset>		Listing: 16.2		Snapshot	Data DD-MMM-YYYY
Program Name: <pg< td="">gm name>	Date: YYYY-MM	-DD Time: HH:MM:SS	Programmer	: <programmer initials=""></programmer>	</pg<>	gm name>	Date: YYYY-MM	-DD Time: HH:MM:SS	Programmer	: <programmer initials=""></programmer>

Protocol: 16-POD-001 Version 2.0, 15-Jan-2018

Confidential

Table 14.2.7.1.1
Warts Area (cm ²) by Visit, PP population

Visit	Statistic	Test Product	Reference	Placebo	All Subjects
Baseline (Day 0)	n	n			
	Mean (SD)	xx.x (xx.xx)			
	CV	XX.X	XX.X	XX.X	XX.X
	Median	XX.X	XX.X	XX.X	XX.X
	Min, Max	XX.X, XX.X	XX.X, XX.X	XX.X, XX.X	XX.X, XX.X
Visit 3 (Day 7)	n				
	Mean (SD)	xx.x (xx.xx)			
	CV	XX.X	XX.X	XX.X	XX.X
	Median	XX.X	XX.X	XX.X	XX.X
	Min, Max	XX.X, XX.X	XX.X, XX.X	XX.X, XX.X	XX.X, XX.X
Visit 3 change from					
baseline	n				
	Mean (SD)	xx.x (xx.xx)			
	CV	XX.X	XX.X	XX.X	XX.X
	Median	XX.X	XX.X	XX.X	XX.X
	Min, Max	XX.X, XX.X	XX.X, XX.X	XX.X, XX.X	XX.X, XX.X
